### 9.5 Analysis Populations

# 9.5.1 Efficacy Analysis Populations

# Full Analysis Set (FAS) Population

The FAS population will serve as the primary population for the evaluation of efficacy and for the estimation of incidence of RSV-associated disease. The FAS population consists of all randomized participants who receive 1 dose of study treatment. Participants will be included in the treatment group corresponding to the study treatment they were randomized to for the analysis using the FAS population.

For an episode of respiratory infection to be considered for evaluation of an efficacy endpoint for the analysis in the FAS population, a PCR result from the study central laboratory must be available for an NP sample that is collected no more than 12 days after symptom onset or symptom worsening, or after symptom onset and no more than 7 days before symptom worsening. A sensitivity analysis will be conducted, which will include PCR results from NP samples collected within the timeframe mentioned above, but not tested at the study central laboratory.

## Per-Protocol Efficacy (PPE) Population

The PPE population will serve as a supportive analysis population for the evaluation of efficacy and for the estimation of incidence of RSV-associated disease. To be eligible for inclusion in the PPE population, study participants must satisfy the following criteria:

- Receive 1 dose of the correct clinical material corresponding to the treatment group the participants were randomized into,
- Have at least 1 follow-up visit/phone call for assessment of RSV disease, and
- At any time during dosing or efficacy follow-up, do not experience a protocol deviation that may interfere with the assessment of protection against RSV infection conferred by MK-1654.

PRODUCT: MK-1654

PROTOCOL/AMENDMENT NO.: 004-05

The final determination on important protocol deviations, and thereby the composition of the PPE population, will be made prior to the final unblinding of the database and will be documented in a separate memo.

For an episode of respiratory infection to be considered for evaluation of an efficacy endpoint for the analysis in the PPE population, a PCR result from the study central laboratory must be available for an NP sample that is collected no more than 12 days after symptom onset or symptom worsening, or after symptom onset and no more than 7 days before symptom worsening.

For both analysis populations, if a participant with symptoms of respiratory infection prior to dosing has an NP sample collected predose on Day 1 or any subsequent NP samples collected for this episode that are PCR positive for RSV, this episode will not be counted as a case toward the efficacy endpoints.

# 9.5.2 Immunogenicity and Pharmacodynamic Analysis Populations

The immunogenicity and pharmacodynamic analysis populations that will be used in tertiary analyses of immunogenicity and pharmacodynamic endpoints will be described in the sSAP that will be written for this study.

### 9.5.3 Pharmacokinetic Analysis Populations

The PK analysis populations that will be used in tertiary analyses of PK will be described in the sSAP that will be written for this study.

## 9.5.4 Safety Analysis Populations

Safety Analyses will be conducted in the APaT population, which consists of all randomized participants who received a dose of study treatment. Participants will be included in the treatment group corresponding to the study treatment they actually received for the analysis of safety data using the APaT population.

#### 9.6 Statistical Methods

Statistical testing and inference relating to efficacy are described in Section 9.6.1. Statistical methods relating to safety analyses are described in Section 9.6.2. Demographic and baseline characteristics are described in Section 9.6.3. Statistical methods relating to immunogenicity and PK analyses are described in the sSAP. Efficacy results that will be deemed to be statistically significant after consideration of the Type 1 error control strategy are described in Section 9.8. Nominal p-values may be computed for other efficacy analyses, but should be interpreted with caution due to potential issues of multiplicity, sample size, etc.

#### 9.6.1 Statistical Methods for Efficacy Analyses

To address the primary efficacy hypothesis, a 1-sided test of the null hypothesis that the efficacy is  $\leq$ 25% versus the alternative that efficacy is  $\geq$ 25% will be conducted. The primary efficacy hypothesis will be tested at 1-sided  $\alpha$ =0.025 level (ie, 2.5% Type 1 error). Efficacy is defined as:

$$E\% = 100*\{1-(Rt/Rp)\}$$

where Rt and Rp are the incidence rates of RSV-associated MALRI in the MK-1654 and placebo groups, respectively. The incidence rate Rt is defined as Rt=Ct/Tt, where Ct=the count of RSV-associated MALRI cases in the MK-1654 group and Tt=total person-time of follow-up for efficacy in the MK-1654 group. The incidence rate Rp is defined similarly. The 95% CI for E is denoted as (EL, EU), and the statistical criterion for success with respect to the primary efficacy hypothesis will be met if EL >25%.

A modified Poisson regression approach with robust variance [Zou, G. 2004] will be used for the efficacy analyses. The mean and 95% CI of relative risk, Rt/Rp, will be obtained from the model, and will be used to estimate the mean and 95% CI of E. The modified Poisson regression model will include treatment group, and stratification variables of region (Southern Hemisphere and Northern Hemisphere), gestational age (early and moderate preterm infants [ $\geq$ 29 to <35 weeks gestational age] and late pre-term and full-term infants [ $\geq$ 35 weeks gestational age]), and chronological age at the time of consent (<6 months;  $\geq$ 6 months) as covariates. To allow for differences in follow-up times among the participants, log (follow-up time) as the offset term will be added in the modified Poisson regression.

If the number of participants in any stratum is too small and/or convergence cannot be achieved for either of the primary and secondary efficacy endpoints, the covariate will be excluded from the model for the final analysis of all primary and secondary efficacy endpoints. If convergence issues persist, additional covariates will be excluded from the model in the following order: region, chronological age, and gestational age, until the model converges for all primary and secondary efficacy endpoints. Therefore, the same set of covariates will be used in the models for all of the primary and secondary efficacy endpoints in the final analyses.

For the primary analyses of efficacy, cases of RSV-associated outpatient and inpatient MALRI will be counted starting at Day 1 postdose and through 150 days postdose. For the primary efficacy hypothesis, cases of both RSV A and RSV B associated MALRI will be counted as endpoints. The efficacy of MK-1654 against RSV A and RSV B associated MALRI will also be estimated separately.

For the secondary efficacy hypothesis of RSV-associated hospitalization from Days 1 through 150 postdose, the statistical criterion for success will be met if EL >0%. For the secondary efficacy endpoint of RSV-associated outpatient and inpatient MALRI occurring from Days 1 through 180 postdose, the estimate of efficacy and corresponding 95% CI will be provided. The analysis strategy for key efficacy variables is summarized in Table 6.

PRODUCT: MK-1654

PROTOCOL/AMENDMENT NO.: 004-05

Table 6 Analysis Strategy for Key Efficacy Variables

Endpoint/Variable (Description, Time Point)	Primary vs. Supportive Approach	Statistical Method a	Analysis Population	Missing Data Approach		
	Prir	nary Endpoint				
Incidence of RSV-associated outpatient and inpatient MALRI from Days 1 through 150 postdose	P/S	Modified Poisson regression (estimate, 95% CI, P-value)	FAS/PPE	Missing data will not be imputed		
	Secondary Endpoints					
Incidence of RSV-associated hospitalization from Days 1 through 150 postdose	P/S	Modified Poisson regression (estimate, 95% CI, P-value)	FAS/PPE	Missing data will not be imputed		
Incidence of RSV-associated outpatient and inpatient MALRI from Days 1 through 180 postdose	P/S	Modified Poisson regression (estimate, 95% CI)	FAS/PPE	Missing data will not be imputed		

CI=confidence interval; FAS=Full Analysis Set; MALRI=medically attended lower respiratory infection; P=primary approach; PPE=per-protocol efficacy; S=supportive approach; RSV=respiratory syncytial virus.

a The statistical methods are described in Section 9.6.1.

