
 
To evaluate the efficacy of MK-1654 compared to placebo as assessed by the incidence of RSV-associated hospitalization from Days 1 through 150 postdose.
 
Hypothesis: Administration of MK-1654 reduces the incidence of RSV-associated hospitalization from Days 1 through 150 postdose compared to placebo (The statistical criterion for success requires the lower limit of the 95% CI for efficacy to be greater than 0%).
 
	
 
RSV-associated hospitalization, defined as the following:
 
Hospital admission for respiratory illness; AND
 
RSV-positive RT-PCR NP sample
 

To estimate the efficacy of MK-1654 compared to placebo as assessed by the incidence of RSV-associated MALRI (outpatient and inpatient) from Days 1 through 180 postdose.	RSV-associated MALRI (outpatient and inpatient), defined as above
Tertiary/Exploratory	
To estimate the efficacy of MK-1654 compared to placebo as assessed by the incidence of RSV-associated severe MALRI (outpatient and inpatient) from Days 1 through 150 postdose.	
 
RSV-associated severe MALRI, defined as the following seen in an outpatient or inpatient clinical setting:
 
Cough or difficulty breathing; AND
 
1 or more of the following: wheezing, chest wall in-drawing/retractions, rales/crackles, tachypnea, dehydration due to respiratory symptoms; AND
 
Severe hypoxemia or the need for high flow nasal cannula, oxygen mask, or mechanical ventilatory support; AND
 
RSV-positive RT-PCR NP sample
 

**C** Confidential

Objectives	Endpoints
To estimate the efficacy of MK-1654 compared to placebo as assessed by the incidence of RSV-associated hospitalization from Days 1 through 180 postdose.	RSV-associated hospitalization, defined as above
To estimate the incidence of MALRI (outpatient and inpatient) due to any cause from Days 1 through 150 postdose for the MK-1654 and placebo groups.	MALRI (outpatient and inpatient) due to any cause, defined as above
To describe the incidence of RSV-associated MALRI (outpatient and inpatient) from Days 365 through 515 postdose for the MK-1654 and placebo groups.	RSV-associated MALRI (outpatient and inpatient), defined as above
• To describe the incidence of RSV-associated hospitalization from Days 365 through 515 postdose for the MK-1654 and placebo groups.	RSV-associated hospitalization, defined as above

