#### 9.10 Subgroup Analyses

The consistency of the treatment effect will be assessed descriptively by category for the classification variables listed below. Efficacy of MK-1654 against RSV-associated MALRI will be estimated separately in (1) Southern Hemisphere and Northern Hemisphere regions; (2) the early and moderate pre-term infants ( $\geq$ 29 to <35 weeks gestational age) and late pre-term and full-term infants ( $\geq$ 35 weeks gestational age) subgroups; (3) age groups at the time of consent (<6 months;  $\geq$ 6 months); (4) weight groups at the time of consent. In addition to the 2 age groups, efficacy will also be summarized in infants  $\leq$ 2 weeks of age. The incidence of RSV-associated MALRI in each treatment group, the estimate of efficacy, and the nominal 95% CI will be reported for each subgroup.

Subgroup analyses of safety and PK profiles will be summarized descriptively by age groups at randomization. The descriptive statistics will be reported for each subgroup.

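### The stated robust Poisson interval collapses near 100% when the MK-1654 arm has zero cases; small subgroups and rare tertiary endpoints need a rule for this in the sSAP

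*Combined protocol and SAP*

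**What the plan says.** Section 9.6 directs the reader: "Statistical testing and inference relating to efficacy are described in Section 9.6.1". Section 9.6.1 then applies "A modified Poisson regression approach with robust variance" to the efficacy analyses, with log follow-up time as offset and the three stratification factors as covariates. On the interval it says: "The mean and 95% CI of relative risk, Rt/Rp, will be obtained from the model". Table 6 names this model for the primary and the two secondary endpoints.

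The only contingency is for sparse strata or failed convergence. Covariates are then removed, in a set order, "until the model converges for all primary and secondary efficacy endpoints". The treatment term is never removed and the interval method does not change.

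Several estimates outside the confirmatory tests will rest on fewer cases:

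- Section 9.6.1: "The efficacy of MK-1654 against RSV A and RSV B associated MALRI will also be estimated separately".
- Section 3, among the tertiary objectives: "To estimate the efficacy of MK-1654 compared to placebo as assessed by the incidence of RSV-associated severe MALRI".
- Section 9.10: "The incidence of RSV-associated MALRI in each treatment group, the estimate of efficacy, and the nominal 95% CI will be reported for each subgroup".
- Section 9.10 also says: "In addition to the 2 age groups, efficacy will also be summarized in infants" no more than 2 weeks old.

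Section 9.7 gives an exact binomial interval for the efficacy estimates at IA#1 and uses the same method for the probabilities in Table 8. It does not extend that method to the final analyses. No section says what to do when an arm has no cases.

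**The concern.** An effective antibody in a small subgroup, or against a rare outcome, can leave the MK-1654 arm with no cases. The stated method then has no finite estimate. It does not fail visibly, though: it can return an extremely narrow interval just under 100%, however few placebo cases lie behind it. A table could show a lower limit above 99% in newborns from three placebo cases, where an exact interval includes negative efficacy. Calling the interval nominal warns about multiplicity; it does not tell the reader that the limit was set by where the fitting routine stopped. Choosing a replacement after unblinding would be a post hoc choice.

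**Working it through.** **Inputs from the plan (Sections 6.3.1, 6.3.2, 9.9.1.1 and 9.9.1.2).** 2200 and 1100 infants, 2:1 allocation, 5% attrition; placebo incidence 10% (MALRI) and 2% (hospitalization); efficacy 70%; at least 600 early and moderate pre-term infants. The share of infants ≤2 weeks old and the incidence of severe MALRI are not given, so ranges are assumed below.

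**The plan's own figures.**
- MALRI cases: 1045 × 0.10 + 2090 × 0.03 = 104.5 + 62.7 = 167.2 (stated 167).
- Hospitalizations: 20.9 + 12.5 = 33.4 (stated 33).
- Simulated hospitalization power, unadjusted model: 92.8% with attrition, 93.9% without (stated 93.6%).
- Table 8 reproduces: 87.0, 43.7, 19.3 and 3.8% at true efficacy 25, 50, 60 and 70%.

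**Why the interval collapses (no covariates, equal follow-up).** If all n1 MK-1654 infants are case-free and their fitted mean is m, that arm adds n1·m²/(n1·m)² = 1/n1 to the robust variance of the log relative risk, for any m > 0. The placebo arm, with Cp cases among n0, adds 1/Cp − 1/n0. Hence SE = √(1/Cp − 1/n0 + 1/n1), however far the coefficient has drifted.

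- 0/104 vs 3/52: SE = √(0.3333 − 0.0192 + 0.0096) = 0.569.
- 0/2090 vs 21/1045: SE = √(0.0476 − 0.0010 + 0.0005) = 0.217.

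**Fitted limits.** The limits come from a statsmodels Poisson GLM with HC0 variance. The exact limit with zero MK-1654 cases is EL = 1 − [pU/(1 − pU)]·(Tp/Tt), with pU = 1 − 0.025^(1/Cp) and Tp/Tt = 1/2.

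| Cases | Tolerance | Coefficient | Fitted lower limit | Exact lower limit |
|---|---|---|---|---|
| 0/104 vs 3/52 | 1e-2 | −7.79 | 99.87% | −21.0% |
| 0/104 vs 3/52 | 1e-4 | −12.79 | 99.999% | −21.0% |
| 0/104 vs 3/52 | 1e-8 | −21.79 | 99.9999999% | −21.0% |
| 0/2090 vs 21/1045 | 1e-2 | −9.79 | 99.991% | 90.4% |
| 0/2090 vs 21/1045 | 1e-4 | −14.79 | 99.99994% | 90.4% |

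Every fit in the table reported convergence. Covariate-adjusted fits collapsed in the same way; a few with 1 to 3 placebo cases did not converge at tighter tolerances. Other exact lower limits with zero MK-1654 cases are −166% (2 placebo cases), 24% (4) and 78% (10).

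**How often: infants ≤2 weeks old** (10% incidence, 70% efficacy, assumed share of 3300 × 0.95 infants split 2:1). P(zero MK-1654 cases) = 0.97^n1. The last column is the joint probability with 1 to 3 placebo cases, where the exact limit is below 0%.

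| Share | n1 / n0 | P(zero MK-1654) | P(zero MK-1654, 1–3 placebo) |
|---|---|---|---|
| 15% | 314 / 157 | 0.007% | <0.001% |
| 10% | 209 / 104 | 0.17% | 0.001% |
| 5% | 104 / 52 | 4% | 0.9% |
| 3% | 63 / 31 | 15% | 9% |
| 2% | 42 / 21 | 28% | 21% |

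For the pre-term subgroup, whose minimum size is documented, n1 = 600 × 2/3 × 0.95 = 380 and 0.97^380 = 0.001%. At 90% efficacy it is 0.99^380 = 2.2%.

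**How often: a rare tertiary endpoint** (2090 vs 1045, 70% efficacy, assumed placebo incidence p). P(zero MK-1654 and at least one placebo case) = (1 − 0.3p)^2090 × [1 − (1 − p)^1045] = 0.2%, 4%, 25% and 35% at p = 1%, 0.5%, 0.2% and 0.1%.

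**Confirmatory endpoints.**
- Primary MALRI: P(zero MK-1654 cases) is 0.995^2090 = 0.003% even at 95% efficacy.
- Hospitalization: P(zero) is 0.0003%, 1.5% and 12% at 70%, 90% and 95% efficacy.
- The EL >0% decision would change only with at most 3 placebo hospitalizations as well, and P(≤3 of 1045 at 2%) = 1.3e-6. The joint probabilities are 4e-12, 2e-8 and 1.6e-7.

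**The case against.** - **The method for these results is inferred.** Table 6 names the model only for the primary and secondary endpoints, and Section 9.10 describes its assessment as descriptive. The model cannot run unchanged within every subgroup: the chronological age factor is constant among infants ≤2 weeks old. This stands in part. Subgroup and tertiary estimates reach Section 9.6.1 only through its general wording. But that is the only interval method the plan gives for final efficacy estimates.
- **The sSAP may already cover it.** It may; it is not among the documents. If so, confirmation is enough.
- **The larger probabilities rest on assumed inputs.** This stands. Section 4.1 asks for infants born in season to be enrolled soon after birth, so a share of 2% or 3% may be too low.
- **A reader would see the counts.** Section 9.10 reports incidence by group beside the estimate, which limits the harm but does not correct the interval.
- **SAS may behave differently.** SAS is the only software the plan names, for its power simulation, and it was not tested. The finite standard error belongs to the sandwich formula; the printed digits and any warning depend on the program.

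A reader might infer that the hospitalization test is in danger. The joint probabilities above rule that out for practical purposes. A reader might also infer that the separate RSV A and RSV B estimates are heavily exposed. The two subtypes together make up the assumed 10% incidence, apart from co-infections. A subtype with 10% of cases has placebo incidence of about 1% and a probability of 0.2%; reaching 25% to 35% needs a subtype with only 2% to 1% of cases.

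**Conclusion.** The gap holds for descriptive results. With zero MK-1654 cases and at least one placebo case, the method as written gives an interval near 100% that carries almost no information about precision, and dropping covariates cannot cure it because treatment is the failing term. The results at risk are small subgroups and rare tertiary endpoints such as severe MALRI. The size depends on shares and incidences that the plan does not state: negligible at the favorable end of the ranges, roughly one in four to one in three at the unfavorable end, and higher if true efficacy exceeds 70%. No confirmatory conclusion, error rate or sample size is affected, so the documents do not support a call for a protocol amendment. This is a low-priority but worthwhile correction.

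**What to change.** Add to the sSAP, before unblinding:

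> For subgroup and tertiary efficacy estimates with zero MK-1654 cases and at least one placebo case, efficacy and its 95% CI come from the exact conditional binomial method named in Section 9.7, adjusted for person-time. If the placebo arm has zero cases, efficacy is reported as not estimable and the case counts are shown.

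The second sentence is needed because the exact method is also degenerate with no placebo cases. Under the same assumptions, zero placebo cases with at least one MK-1654 case has probability about 8% at a 2% subgroup share, and 9% or 16% at 0.2% or 0.1% incidence.

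Section 9 allows changes to nonconfirmatory analyses to be documented in the sSAP, so Section 9.6.1, the common covariate set and its removal order stay as they are. The cost is a short entry and a small program. IA#1 already uses the exact method, but an external statistician runs that analysis, so the sponsor's biostatistics group may need its own code.

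There are two downsides. The exact interval is not adjusted for the stratification factors and is somewhat conservative. The rule also switches only at zero: with one or two MK-1654 cases the planned robust interval is kept, although it can differ from the exact one (lower limits, 209 vs 104 infants: 1 vs 4 cases, −10% robust and −26% exact; 2 vs 5, −1% and −22%; 1 vs 10, 62% and 65%).

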# 9.6.2 Statistical Methods for Safety Analyses

Safety and tolerability will be assessed by clinical review of all relevant parameters including AEs. All safety summaries will be provided separately for the first and second RSV seasons.

The analysis of safety results will follow a tiered approach (Table 7). AEs (specific terms as well as system organ class terms) and events that meet predefined limits of change (PDLCs) in laboratory and vital signs parameters are either pre-specified as "Tier 1" endpoints or will be classified as belonging to "Tier 2" or "Tier 3" based on the observed proportions of participants with an event.

#### **Tier 1 Events**

Safety parameters or AESI that are identified a priori constitute "Tier 1" safety endpoints that will be subject to inferential testing for statistical significance. There are no Tier 1 events for this protocol as no treatment-related SAEs have been observed in the Phase 1 studies of MK-1654.

#### **Tier 2 Events**

Membership in Tier 2 requires that at least 1% participants in any treatment group exhibit the event; OR AEs listed in Table 7. All other AEs will belong to Tier 3. Maximum body temperature will be summarized using Brighton Collaboration cutoffs.

The threshold of at least 1% was chosen to draw clinical meaningful inference. When less than 1% of participants report AEs in both groups, the 95% CI for the between-group difference may exclude zero. However, the clinical significance of these differences is unknown given the small number of participants who report AEs. Because many 95% CIs for Tier 2 events may be provided without adjustment for multiplicity, the CIs should be regarded as a helpful descriptive measure to be used in review, not a formal method for assessing the statistical significance of the between-group differences in AEs.

### **Tier 3 Events**

Safety endpoints that are not Tier 1 or 2 events are considered Tier 3 events. Only point estimates by treatment group are provided for Tier 3 safety parameters.

Table 7 Analysis Strategy for Safety Parameters

Safety Tier	Safety Endpoint	95% CI for Comparison of MK-1654 and Placebo	Descriptive Statistics
Tier 2	Any AE a	X	X
	Any Serious AE	X	X
	Any Drug-related AE	X	X
	Any Serious and Drug-related AE	X	X
	Discontinuation due to AE	X	X
	Solicited Injection-site AEs Days 1-5 Postdose	X	X
	Solicited Daily Body Temperature Days 1-5 Postdose	Х	X
	Solicited Systemic AEs Days 1-5 Postdose	X	X
	Anaphylaxis/hypersensitivity AESI Days 1-42 Postdose	Х	X
	Rash AESI Days 1-42 Postdose	X	X
	Nonserious AEs Days 1-42 Postdose	X	X
	AEs by SOC (incidence ≥1% of participants in 1 of the treatment groups)	Х	X
Tier 3	AEs by SOC (incidence <1% of participants in all of the treatment groups)		X

AE=adverse event; AESI=adverse event(s) of special interest; SAE=serious adverse event; CI=confidence interval; SOC=System Organ Class; X=results will be provided.

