## 9.9 Sample Size and Power Calculations

# 9.9.1 Sample Size and Power for Efficacy Analyses

# 9.9.1.1 Sample Size and Power for Testing the Primary Efficacy Hypothesis

The sample size of approximately 3300 was selected to ensure collection of adequate safety information on the use of MK-1654 in this otherwise healthy population of pre-term and full-term infants. This study will randomize approximately 2200 healthy infants into the MK-1654 group and approximately 1100 healthy infants into the placebo group. A total of approximately 167 cases of RSV-associated MALRI in the MK-1654 and placebo groups are expected to accrue by the end of the study, under the following assumptions: 1) incidence of RSV-associated MALRI in the placebo group is 10% per season; 2) efficacy=70%, so that the incidence of RSV-associated MALRI in the MK-1654 group is 3% per season; and 3) attrition rate is 5%. Under these assumptions, there is >95% power to demonstrate that the efficacy of MK-1654 compared to placebo to prevent RSV-associated MALRI is >25% if the underlying efficacy is 70% at an overall 1-sided Type 1 error of 2.5%. The calculations are based on a simulation study for the modified Poisson regression and carried out using the SAS software.

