# 9.9.2 Sample Size and Power for Safety Analyses

The probability of observing at least 1 SAE in this study depends on the number of participants treated and the underlying percentage of participants with a SAE in the study population. Calculations below assume that 100% of the randomized participants will be evaluable for safety analyses. If the underlying incidence of an SAE is 0.069% (1 of every 1456 participants receiving the MK-1654), there is an 80% chance of observing at least 1 SAE among 2200 participants in the MK-1654 group. If the underlying incidence of an SAE is 0.033% (1 of every 3039 participants receiving the MK-1654), there is a 50% chance of observing at least 1 SAE among 2200 participants in the MK-1654 group. If no SAEs are observed among the 2200 participants in the MK-1654 group, this study will provide 97.5% confidence that the underlying percentage of participants with an SAE is <0.139% (1 in every 720 participants) in the MK-1654 group.

The percentage point differences between the 2 groups that could be detected with 80% probability for a variety of hypothetical underlying incidences of an AE are summarized in Table 9. These calculations assume 2200 participants in the MK-1654 group and 1100 participants in the placebo group and are based on a 2-sided 5% alpha level. The calculations are based on an asymptotic method proposed by Farrington and Manning (1990) [Farrington, C. P. 1990]; no multiplicity adjustments were made.

Table 9 Differences in Incidence of Adverse Event Rates Between the 2 Groups That can be Detected With an ~80% Probability (Assuming 2-sided 5% Alpha Level With 2200 Participants in the MK-1654 Group and 1100 Participants in the Placebo Group)

Incidence of	Incidence of Adverse Event		
Placebo (%)	MK-1654 (%)	Percentage Points	
0.1	0.8	0.7	
2.0	3.8	1.8	
5.0	7.5	2.5	
10.0	13.3	3.3	
15.0	18.9	3.9	
20.0	24.3	4.3	
30.0	34.9	4.9	

Incidences presented here are hypothetical and do not represent actual adverse experiences in either group. Based on an asymptotic method [Farrington, C. P. 1990].

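### For adverse events not named in Table 7, the first row of Table 9 (0.1% vs 0.8%, about 80% detectable) describes a comparison that the 1% tier rule would produce in only about 17% of trials

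*Combined protocol and SAP*

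**What the plan says.** **Detection figure.** Section 9.9.2 introduces Table 9 as "The percentage point differences between the 2 groups that could be detected with 80% probability" over a range of hypothetical underlying incidences, and the table title repeats "That can be Detected With an ~80% Probability". The first row is 0.1% on placebo, 0.8% on MK-1654, a difference of 0.7 points. The stated conditions are "These calculations assume 2200 participants in the MK-1654 group and 1100" on placebo; the calculations "are based on a 2-sided 5% alpha level", use the Farrington-Manning asymptotic method and make no multiplicity adjustment. For evaluability: "Calculations below assume that 100% of the randomized participants will be evaluable for safety analyses".

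**Planned comparison.** Section 9.6.2 tiers both specific AE terms and system organ classes. There are no Tier 1 events, so no safety endpoint is formally tested. An event enters Tier 2 and gets a between-group 95% CI if at least 1% of either group has it, or if Table 7 lists it. Everything else is Tier 3: "Only point estimates by treatment group are provided for Tier 3 safety parameters".

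**Exempt from the 1% rule.** Table 7 lists these with no incidence threshold: any AE, any serious AE, any drug-related AE, any serious and drug-related AE, discontinuation due to AE, the three solicited categories, anaphylaxis/hypersensitivity AESI, rash AESI, and nonserious AEs.

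**Reason given for the cut-off.** The Tier 2 text says: "When less than 1% of participants report AEs in both groups, the 95% CI for the between-group difference may exclude zero". It then adds that the clinical meaning of such a difference is unknown when so few participants are involved.

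**The concern.** Both rates in the first row of Table 9 lie below 1%, and the row is offered for an AE in general. For an event that Table 7 does not name, the Tier 2 CI is the only between-group comparison planned, and it appears only if the observed rate reaches 1% in an arm. A true rate of 0.8% will usually not get there. The row then credits the planned safety analysis with a sensitivity it does not have for those events.

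This deserves correcting because section 9.9.1.1 rests the trial's size on safety: "The sample size of approximately 3300 was selected to ensure collection of adequate safety information". A reader relying on Table 9 would expect an imbalance of that size in a specific term or organ class to come with an interval. Usually it would not.

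**Working it through.** **Inputs.** From 9.9.2: 2200 on MK-1654, 1100 on placebo, two-sided 5%, all randomized participants evaluable, true rates 0.1% and 0.8%. From 9.6.2: the 1% threshold, which means at least 22 of 2200 or at least 11 of 1100.

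**Step 1. Reproduce the row.** Score approach with zero null difference:
- Pooled rate = (1100 × 0.001 + 2200 × 0.008)/3300 = 18.7/3300 = 0.005667.
- Null SE = √[0.005667 × 0.994333 × (1/1100 + 1/2200)] = 0.002772.
- Alternative SE = √[0.001 × 0.999/1100 + 0.008 × 0.992/2200] = 0.002125.
- Power = Φ[(0.007 − 1.96 × 0.002772)/0.002125] = Φ(0.737) = 77.0%.

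Power of exactly 80% is reached at 0.837%, which prints as 0.8, so the row reproduces within rounding. Rows 2 to 7 give 81.5%, 78.9%, 78.9%, 79.9%, 79.8% and 80.8%. Exact binomial enumeration of the score test at 0.1% vs 0.8% gives 84.4%. Table 9 contains no arithmetic error.

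**Step 2. Apply the tier rule to an event not named in Table 7.**
- Expected MK-1654 count = 2200 × 0.008 = 17.6, against a threshold of 22.
- P(X ≥ 22), X ~ Binomial(2200, 0.008) = 17.4%.
- P(Y ≥ 11), Y ~ Binomial(1100, 0.001) is below 1 in 10 million.
- P(a CI is produced) = 17.4%; P(point estimates only) = 82.6%.

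Rounding range of the printed 0.8%: 11.1% at a true rate of 0.75%, 25.1% at 0.85%. The true MK-1654 rate would have to be about 0.98% for an even chance of a CI and 1.17% for an 80% chance. With 10% over-enrollment (2420 on MK-1654, threshold 25), the 17.4% falls to 12.3%.

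**Step 3. Combine the two (exact enumeration at 0.1% vs 0.8%).**

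| Outcome | Probability |
|---|---|
| Score test significant | 84.4% |
| Significant and in Tier 2 | 17.2% |
| Significant but in Tier 3, no CI | 67.2% |

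So 67.2/84.4 = 79.6% of significant results would carry no interval.

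**Step 4. What Tier 3 looks like (Miettinen-Nurminen 95% CI, MK-1654 minus placebo, percentage points).**

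| MK-1654 of 2200 vs placebo of 1100 | 95% CI | Shown under the plan? |
|---|---|---|
| 18 vs 1 | 0.25 to 1.21 | No |
| 21 vs 0 | 0.61 to 1.46 | No |
| 8 vs 0 | excludes zero | No |
| 7 vs 0 | −0.03 to 0.66 | No |
| 4 vs 0 | −0.17 to 0.47 | No |
| 0 vs 2 | −0.66 to −0.01 | No |

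**Step 5. Scope.** At 2.0% vs 3.8%, the second row, Tier 2 entry is essentially certain, so only the first row is affected. For a category that Table 7 lists at any incidence the CI is always produced, and the roughly 80% stands.

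**The case against.** The case for leaving the plan alone is substantial, and most of it stands.

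- **Exempt categories.** A reader might infer that no adverse event below 1% is ever compared between groups. The documents do not support that. Table 7 compares serious AEs, discontinuations and both AESI categories at any incidence, and hypersensitivity and rash are the class risks the protocol itself names (4.2.1.2).
- **A disclosed choice.** A reader might infer that the cut-off exists to suppress intervals that exclude zero. The plan foresees such intervals, says so, and gives unknown clinical significance with few participants as its reason. This is a stated judgement, not a hidden gap.
- **Imbalances stay visible.** Tier 3 still reports both arms' point estimates, so 18 vs 1 would be seen. The eDMC also reviews safety at least every 6 months during enrollment (9.7). Only the interval is lost.
- **Table 9 is illustrative.** Its incidences are labelled hypothetical, Tier 2 CIs are called descriptive, and 9.9.1.1 does not cite Table 9 as the basis for the sample size.

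What does not stand is that the exempt rows fully replace term-level comparison. Hospitalization makes an event serious (10.3.3), and 8.4.6 excludes no disease-related events. The any-serious-AE row therefore includes RSV hospitalizations, assumed in 9.9.1.2 to be 2% on placebo and 0.6% on MK-1654. That 1.4-point benefit could outweigh a 0.7-point excess of one specific SAE within the composite. The disclosed rationale also does not tell a reader of 9.9.2 that the first row excludes unlisted events.

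**Conclusion.** The point holds for AEs that Table 7 does not list by name, that is, individual terms and system organ classes. For these, the first row of Table 9 does not describe the planned analysis: a between-group CI would appear in about 17% of trials (11% to 25% over the rounding range), against about 84% in which a score test would be significant. It does not hold for the listed Table 7 categories, or for rows 2 to 7.

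The figures assume true rates of 0.1% and 0.8%, arms of 1100 and 2200, full evaluability as 9.9.2 states, and independent binomial counts. Severity is minor: this is a mismatch between a stated detection figure and the output for one class of events. No efficacy conclusion changes.

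**What to change.** Either change resolves it.

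**(a) Extend the comparison.** In 9.6.2 and Table 7, add descriptive Miettinen-Nurminen 95% CIs for SAE terms, and for AE terms and system organ classes below 1% in both arms. If a minimum count is wanted to limit table length, derive it from the 2:1 arm sizes. With no events in the other arm, the CI first excludes zero at 8 on MK-1654, but already at 2 on placebo, so one common count does not suit both arms. Cost: SAP wording, extra table rows, and more unadjusted intervals, which 9.6.2 already tells readers to treat as descriptive.

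**(b) Keep the 1% rule and scope the claim.** In 9.9.2, state that the first row of Table 9 applies only to the Table 7 categories compared at any incidence, and that other AEs below 1% in both arms receive point estimates only. Cost: one footnote. A blanket statement that rates below 1% are not compared should be avoided, because it would be false for the listed categories.
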